- Appointment attendance rate (AAR): AAR is the proportion of scheduled visits completed during the observation period. A visit is considered "completed" if the patient visits the clinic on the scheduled appointment date, or up to 7 days before that date. AAR is computed from clinic records. Measurement window truncated to last visit date for patients who transfer clinics, opt out of future study participation, or die.
- Lost to follow-up (LTFU): LTFU is a binary variable equal to 1 if a patient missed the last appointment and 90 or more days have elapsed since the patient's last scheduled appointment date, with no clinic record of contact since that date; and 0 otherwise. Patients who transfer clinics or opt out of future study participation are excluded from the LTFU denominator, but those who die are retained in the LTFU denominator.

Control variables

Regression specifications for analysis of treatment effects we will also include control variables to absorb residual variation and reduce standard errors of estimates. The control variables will be:

- Indicator: respondent is female
- Indicator: respondent is married
- Age (in years)
- Completed education (in years)
- One way travel time to clinic (in minutes)
- Knowledge about risk of missing ART doses (fraction of 4 questions answered correctly; takes on values of 0, .25, .5, .75, 1)¹
- Indicator: respondent is food insecure (ever skipped or reduced meal size in the last 12 months)
- Indicator variables for day of week of enrollment (one indicator for each of the following days of week: Monday, Tuesday, Wednesday, Thursday; Friday omitted)
- Indicator variable for enumerator (project staff member) administering enrollment and baseline survey (one indicator variable for each enumerator)

Because respondents are allowed to skip questions on the baseline survey, there may be missing values for some of these control variables. If any missing value exists for some variable “X”, we will create an indicator variable for variable X to flag missing status (1 if missing, 0 otherwise), replace the missing value of the variable X with zero, and include the variable X missing indicator variable in the set of control variables.

Data Adjustments to Be Conducted While Blind to Treatment Assignment

Observations will be excluded from the sample for analysis under the following circumstances.

1. MPR cannot be calculated
2. Three (3) or more control variables are missing values.

Balance Tests

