- Above or equal to median education vs. Below median education
- Food insecure vs. Not food insecure²
- Above or equal to median distance to the clinic vs. Below median distance to the clinic
- Above or equal to median knowledge about the risk of missing doses vs. Below median knowledge about the risk of missing doses

To correct for multiple hypothesis testing in this subgroup analysis, we will also use the method of List, Shaikh, and Xu (2016), accounting simultaneously for multiple subgroups and multiple treatments.

References

Bonferroni, C. E., *Il calcolo delle assicurazioni su gruppi di teste*. Tipografia del Senato, 1935.

Holm, S., "A Simple Sequentially Rejective Multiple Test Procedure," *Scandinavian Journal of Statistics*, 1979, pp. 65-70.

List, John, Azeem Shaikh, and Yang Xu, "Multiple Hypothesis Testing in Experimental Economics," NBER Working Paper 21875, January 2016.

² Food insecure is defined, as in the control variable, as having skipped or reduced the size of meals in the household in the last 12 months.

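### Exclusion rule 2 drops randomised participants with an observed primary outcome because precision-only baseline controls are missing, although the plan's own missing-indicator rule could keep them

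*SAP*

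**What the plan says.** Under Data Adjustments to Be Conducted While Blind to Treatment Assignment, the SAP states that "Observations will be excluded from the sample for analysis under the following circumstances". It then lists two separate circumstances:

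- Rule 1: "MPR cannot be calculated".
- Rule 2: "Three (3) or more control variables are missing values".

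Under Control variables, it gives the purpose of the covariates: the regressions will "include control variables to absorb residual variation and reduce standard errors of estimates". The same section notes that respondents may skip baseline survey questions. For any variable with a missing value the plan is to "replace the missing value of the variable X with zero, and include the variable X missing indicator variable in the set of control variables". That paragraph sets no upper limit on missing items per participant.

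The primary outcome does not depend on the survey. Under Primary Outcome of Interest and Hypotheses, MPR is derived from pharmacy dispensing data. One control, knowledge about missed doses, is a composite: "fraction of 4 questions answered correctly".

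**The concern.** Rule 1 already deals with a missing outcome. Rule 2 on its own therefore affects only people who were randomised and whose MPR can be computed. They are discarded because they skipped survey items that enter the model solely to tighten the estimates. A device meant to gain precision is used in a way that loses it.

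The SAP does not say why zero-fill with a flag is adequate for two missing controls but not for three, and it plans no analysis that keeps the excluded people. The exclusion applies to the analysis sample in general, so it reaches the primary, secondary and subgroup results.

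Two things are at stake: precision in the full-sample regressions, and the population described, which narrows from everyone randomised with an observed outcome to those who answered most of the survey. In addition, the SAP does not say whether one skipped question out of four makes the knowledge control missing, so the set of people who reach three is not fully determined.

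**Working it through.** The SAP gives no sample size, skip rate or power figure, so there is no stated number to reproduce. The check has two parts: reading the rules together, and bounding the size under stated assumptions.

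**Reading the rules together.** A participant with a calculable MPR and one or two missing controls is kept by zero-fill and flags. With three or more, the same treatment could be applied, but rule 2 removes the person first. The rules are compatible in sequence, and the exclusion is a choice that the missing-data method does not require.

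**Inputs for the size.** Seven controls describe the respondent: sex, marital status, age, education, travel time, knowledge and food insecurity. Day of enrolment and enumerator are left out of the count, on the assumption that staff record them. The item skip rate *p* is assumed to be 2%, 5% or 10%, the same for all seven. If a fraction *f* is excluded, standard errors widen by 1/√(1−f) − 1.

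**(a) Independent skipping.** f = P(X ≥ 3), X ~ Binomial(7, p).

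**(b) Independent skipping, knowledge missing if any of its four questions is skipped.** The knowledge control is then missing with probability q = 1 − (1−p)⁴ = 7.8%, 18.5% or 34.4%. With Y ~ Binomial(6, p) for the other six controls, f = P(Y ≥ 3) + q·P(Y = 2). At p = 10% this is 1.585% + 0.3439 × 9.84% = 4.97%.

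**(c) Clustered skipping.** X is beta-binomial with 7 items, mean p and assumed intra-person correlation ρ = 0.3, that is, with parameters p(1−ρ)/ρ and (1−p)(1−ρ)/ρ.

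| Scenario | p = 2% | p = 5% | p = 10% |
|---|---|---|---|
| (a) excluded | 0.03% | 0.38% | 2.57% |
| (a) wider SE | 0.01% | 0.19% | 1.31% |
| (b) excluded | 0.06% | 0.79% | 4.97% |
| (b) wider SE | 0.03% | 0.40% | 2.58% |
| (c) excluded, ρ = 0.3 | 1.83% | 4.80% | 10.31% |
| (c) wider SE, ρ = 0.3 | 0.93% | 2.49% | 5.59% |
| (c) excluded, ρ = 0.1 | 0.7% | 2.4% | 6.5% |
| (c) wider SE, ρ = 0.1 | 0.4% | 1.2% | 3.4% |

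**Do the extra flags use up the precision regained?** Simulations of the planned regression, with seven controls and seven flags, say no. All sample sizes are assumed.

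- Four equal arms, binary outcome, ρ = 0.3, 1,500 runs, true effect zero. The empirical SD of β₁ under rule 2, relative to keeping everyone, was 1.009, 1.029 and 1.052 at n = 400 and 1.011, 1.016 and 1.061 at n = 1,000 (p = 2%, 5%, 10%). The mean of β₁ was within 0.002 of zero either way.
- n = 800, skipping clustered and related to the outcome, true effects 0.10, 0.05 and 0.15. Rule 2 excluded about 7.9%. Mean estimates were 0.099, 0.049 and 0.149 with and without it. SDs were 0.048, 0.051 and 0.047 keeping everyone, against 0.051, 0.053 and 0.049 under rule 2. The design was full rank in every run.
- ρ = 0.3, skipping related to the outcome, n = 100–200 (about the size a subgroup might have) and n = 400–1,000. SD ratios were 1.00 to 1.08 in favour of keeping everyone, with no visible bias.

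**The case against.** The strongest defence is that rule 2 is coherent, objective, prespecified, based on baseline items and applied blind. It contradicts nothing, and plans often set a threshold without giving a reason. Its effect may be negligible: with independent skipping at 2% or 5%, standard errors widen by 0.2% at most. The larger figures need both clustering and fairly heavy skipping, and a common skip rate for all seven items is doubtful for sex and age. A single sensitivity analysis retaining the excluded people might be enough.

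Most of this stands as a limit on severity. It does not justify discarding observed outcomes. Blinding protects against selective exclusion but gives no reason to exclude. If few people are affected, removing the rule costs almost nothing; if many are, it matters.

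The fixed denominator of four also allows a skipped knowledge question to count simply as not correct. That reading is possible but unstated, and the definition is needed for the missing flag whether or not rule 2 stays. It is a minor accompanying gap and the main point does not depend on it.

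The gain for the subgroup analyses is limited. Someone missing the item that defines a pair, such as "Above or equal to median education vs. Below median education", cannot be placed in that pair under either approach.

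**Conclusion.** The concern holds, as an avoidable exclusion after randomisation. It is neither a contradiction nor a demonstrated source of bias. The absence of bias assumes that survey answers were given before assignment or were unaffected by it; the SAP does not state the order of survey and randomisation.

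The loss ranges from trivial to moderate: from 0.03% excluded (independent skipping at 2%) to 10.3% excluded with standard errors 5.6% wider (10% skipping, correlation 0.3). Both the skip rates and the correlation are assumptions. In every simulated setting keeping everyone was at least as precise as excluding. The change should be made, with medium confidence about its practical importance.

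**What to change.** Replace exclusion rule 2 with text to this effect:

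> No participant is excluded for missing control variables. Everyone with a calculable MPR is analysed under the missing-indicator rule; identical or collinear missing indicators are merged or dropped. Medians and subgroup membership use observed values only, never zero-filled ones; a participant missing the defining variable is left out of that subgroup pair only. We report by arm the number missing three or more controls and repeat the primary regression without them as a sensitivity analysis.

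The sentence on medians and subgroups is a safeguard for the people now retained; the SAP does not say that zero-filled values would be used there. Also state whether one skipped knowledge question makes the score missing or counts as not correct.

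The cost is one documented, dated change and no new data. It should be made while the analysts are still blind to assignment; the SAP alone does not show whether that is still possible. The remaining downside is a few sparse missing indicators, mainly in the subgroup regressions.
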